Appendix B - ACTT-2: Baricitinib/Remdesivir vs Remdesivir

clinical outcome measure of Day 2 is captured with the worst being death followed by ECMO, mechanical ventilation, etc. The Day 2 measurement is assessed as occurring anytime in that 24-hour period (00:00 to 23:59).

It is important to capture all deaths that occur during the study as this is one of the outcomes of the study. Death is a category on the ordinal scale. If a subject dies during the study, the site will need to complete an ordinal scale assessment for the day after death. If a subject dies within the window of the final study visit (i.e., Day 29 \pm 3 days), complete an ordinal scale assessment on the day after death.

For more information about the data collected for the ordinal scale, see the MOP.

8.1.2.3 National Early Warning Score (NEWS)

Vital signs and other clinical assessments are collected for the calculation of the NEWS, and include temperature, systolic blood pressure, heart rate, respiratory rate, O₂ saturation and level of consciousness. Vital signs collected per standard of care can be used. NEWS has demonstrated an ability to discriminate subjects at risk of poor outcomes. (Smith, 2016). This score is based on 7 clinical parameters (see Table 2). The NEWS is being used as an efficacy measure. The NEWS should be evaluated daily while hospitalized and on Days 15 and 29. It can be performed concurrently with the Ordinal Scale. This should be evaluated at a consistent time for each study day and prior to administration of study product. The 7 parameters can be obtained from the hospital chart or electronic medical record (EMR) using the last measurement prior to the time of assessment (including parameters collected prior to the time of consent) and a numeric score is given for each parameter (e.g., a RR of 9 is one point, oxygen saturation of 92 is two points). This is recorded for the day obtained (i.e., on Day 3, the vital signs and other parameters from Day 3 are used to obtain NEWS for Day 3). ECMO and mechanically ventilated subjects should be assigned a score of 3 for RR (RR $<$ 8) regardless of the ventilator setting. Subjects on ECMO should get a score of 3 for heart rate since they are on cardiopulmonary bypass.

Table 2. National Early Warning Score (NEWS)

Appendix B - ACTT-2: Baricitinib/Remdesivir vs Remdesivir

PHYSIOLOGICAL PARAMETERS	3	2	1	0	1	2	3
Respiration Rate	≤8		9 - 11	12 - 20		21 - 24	≥25
Oxygen Saturations	≤91	92 - 93	94 - 95	≥96			
Any Supplemental Oxygen		Yes		No			
Temperature	≤35.0		35.1 - 36.0	36.1 - 38.0	38.1 - 39.0	≥39.1	
Systolic BP	≤90	91 - 100	101 - 110	111 - 219			≥220
Heart Rate	≤40		41 - 50	51 - 90	91 - 110	111 - 130	≥131
Level of Consciousness				A			V, P, or U

Level of consciousness = alert (A), and non-alert and arousable only to voice (V) or pain (P), and unresponsive (U).

If the subject is on ECMO or invasive mechanical ventilation, they will be given score of 3 (≤8 RR) for respiratory rate regardless of ventilator setting. For subjects on ECMO, they will also receive a score of 3 (≤40 HR) for heart rate.

8.1.3 Exploratory assessments

8.1.3.1 Viral Load and/or Shedding

As outlined on the SOA, OP samples (collected by swab) and plasma and serum will be collected on Day 1; and Days 3, 5, 8, and 11 (while hospitalized); and OP swabs and serum on Day 15 and 29 (if attends an in- person visit or still hospitalized). Samples are stored as outlined in the MOP. These assays are not developed yet, and the ability to test samples at one central lab is not clear. Therefore, while viral load/shedding is thought to be an important endpoint, considering the limitations above, it is listed as an exploratory endpoint.

OP samples are preferred, but if these are not obtainable, nasopharyngeal (NP) samples (collected by NP swab) or nasal swab may be substituted. Due to limited lack of swabs and other supplies at some sites and limitations on personal protective equipment (PPE), the inability to obtain these samples are not considered protocol deviations and should be documented in the subject's record.

If virology assays can be set up with enough numbers of specimens tested, these data will be submitted as part of the Clinical Study Report (CSR). This may be submitted separately, as a supplemental CSR.

Samples collected for viral assessment may be probed for the emergence of antiviral resistance at a future date. These data, if available, may be submitted as a supplement report.

The schedule of assessments (SOA, Section 1.2) lists several research laboratory samples. It is preferred that these samples are collected and sent to the NIAID repository to be tested in one central laboratory. Current US Centers for Disease Control and Prevention (CDC) guidance is these samples can be processed in a Biosafety Laboratory (BSL) 2 environment. However, institutions may impose restrictions on processing the samples (i.e., they may require BSL-3) or there may be restrictions on sending samples. In these circumstances, the following apply:

Blood for PCR SARS-CoV-2

- If the samples can be processed but cannot be sent to the repository, the samples may be stored locally.
- The sponsor may elect to have some or all of these samples run locally, pending confirmation of the assays to be used and the qualifications of the local laboratory. The sponsor will work with the site to determine when this could occur and how these data can be imported into the study database.
- If a BSL-3 environment is needed for processing these samples, these samples may be omitted.

Oropharyngeal or Nasopharyngeal/nasal specimen

- If the samples can be processed but cannot be sent to the repository, the samples may be stored locally.
- The sponsor may elect to have some or all of these samples run locally, pending confirmation of the assays to be used and the qualifications of the local laboratory. The sponsor will work with the site to determine when this could occur and how these data can be imported into the study database.
- If a BSL-3 environment is needed for processing these samples, these samples may be omitted.

Blood for serum (for secondary research)

- If the samples can be processed and but not sent to the repository, the samples may be stored locally.
- If a BSL-3 environment is needed for processing these samples, these samples may be omitted.

8.1.3.2 Cytokine Assessments

To assess the impact of baricitinib on serum cytokine levels, blood samples will be assessed using a multiplex assay that is less sensitive to variability in sample integrity due to sample processing limitations during the pandemic. Cytokines to be tested may include (but not be limited to) IL-2, IL-19, IL-4, IL-10, IL-8, G-CSF, GM-CSF, MCP-1, MIP1 α , IL-7, IL-13, IL-31, IL-15, IL-6, IFN α , IFN γ and TNF α . The list of cytokines tested is subject to change as new information about the pro-inflammatory state of COVID-19 is known. Given the challenges of obtaining samples and evolving knowledge about COVID-19, these will be considered exploratory endpoints. The description of the final methodology utilized, and the assay performance characteristics will be included in the final study report.

8.2 Safety and Other Assessments

Appendix B - ACTT-2: Baricitinib/Remdesivir vs Remdesivir

Study procedures are specified in the SOA. A study physician licensed to make medical diagnoses and listed on the 1572 will be responsible for all trial-related medical decisions.

Physical examination:

A targeted physical examination will be performed at baseline prior to initial study product administration on Day 1. The baseline physical examination can be one that is conducted from screening to Day 1. No routine physical exam is needed for study visits after Day 1.

Study staff at some sites are not allowed into the subject’s rooms due to a limited supply of PPE and the need for strict respiratory isolation measures for COVID-19 patients. Because of limited access to subjects, physical exams can be performed by any licensed provider at the study hospital even if they are not study staff listed on the 1572. The study team can extract information from the hospital chart or EMR.

Clinical laboratory evaluations:

- Fasting is not required before collection of laboratory samples.
- Blood will be collected at the time points indicated in the SOA.
 - Clinical safety laboratory tests include WBC, differential, Hgb, PLT, creatinine, glucose, total bilirubin, AST, ALT, INR, d-dimer, and C-reactive protein.
 - Day 1 clinical laboratory evaluations are drawn prior to initial study product administration as a baseline and results do not need to be reviewed to determine if initial study product administration should be given.
- Clinical laboratory testing will be performed at each clinical trial site in real time.

Table 3. Venipuncture Volumes¹

	Screen	Baseline						
Day +/- Window	-1 to 1	1 ± 1	3 ± 1	5 ± 1	8 ± 1	11 ± 1	15 ± 2	29 ± 3
Safety hematology, chemistry and liver tests	X 10mL ²	X ³ 10mL ²	X ³ 10mL ²					
Blood for Serum		X 24mL	X 24mL	X 24mL	X 24mL	X 24mL	X 24mL	X 24mL
Plasma (includes PCR)		X 8mL	X 8mL	X 8mL	X 8mL	X 8mL		
Total volume	10mL	42ml	42mL	42ml	42ml	42ml	34mL	34mL
Total all study days								268~288 mL

1. See SOA in Section 1.2 for specific tests to be performed.
2. Total volume calculated assumes there are no routine clinical laboratory were done within 48 hours of screening that can be used for determining eligibility and no routine clinical laboratory tests were done within the window for that visitor 24 hours of Day 1, 3, 5, 8 and 11 and 48 hours for Day 15 and 72 hours for Day 29 if still hospitalized.
3. Safety laboratory tests will be collected on Day 15 and 29 if the subject is still hospitalized at these time points or if they return for an in-person outpatient visit and the site has the capacity to collect blood in the outpatient setting.

8.2.1 Procedures to be Followed in the Event of Abnormal Laboratory Test Values or Abnormal Clinical Findings

If a physiologic parameter (e.g., vital signs, or laboratory value) is outside of the protocol-specified range, then the measurement may be repeated once if, in the judgment of the

Appendix B - ACTT-2: Baricitinib/Remdesivir vs Remdesivir

investigator, the abnormality is the result of an acute, short-term, rapidly reversible condition or was an error. A physiologic parameter may also be repeated if there is a technical problem with the measurement caused by malfunctioning or an inappropriate measuring device (i.e., inappropriate-sized BP cuff).

8.2.2 Unscheduled Visits

If clinical considerations require the subject to be contacted or seen prior to the next schedule assessment to assure the subject's well-being, it is permissible in this protocol. However, no research data is collected at this visit.

8.3 Adverse Events and Serious Adverse Events

8.3.1 Definition of Adverse Event (AE)

AE means any untoward medical occurrence associated with the use of an intervention in humans, whether or not considered intervention related. An AE can therefore be any unfavorable and unintended sign (including an abnormal laboratory finding), symptom, or disease temporally associated with the use of medicinal (investigational) product. If multiple abnormalities are part of the same clinical syndrome, they can be reported together as one AE under a unifying clinical diagnosis.

Any medical condition that is present at the time that the subject is screened will be considered as baseline and not reported as an AE. However, if the severity of any pre-existing (baseline) medical condition increases above baseline to severity grade 3 or 4, it should be recorded as an AE.

Given the nature of severity of the underlying illness, subjects will have many symptoms and abnormalities in vital signs and laboratory values. Only Grade 3 and 4 AEs will be captured in this trial. In addition, the following AEs will be reported:

- Any Grade 2 or higher suspected drug-related hypersensitivity reactions associated with study product administration will be reported as an AE.
- Any venous thromboembolism at any time during the study.

Unsolicited-laboratory values collected as part of standard of care, will need to be reported only if Grade 3 or above and only if clinically significant and/or part of a diagnosis or a clinical syndrome. In this case, if laboratory and vital sign abnormalities are part of the clinical syndrome, they should be reported as one AE under one clinical diagnosis or syndrome. Example: Low oxygen level/arterial blood gases could be part of respiratory failure diagnosis.

Intermittent abnormal laboratory values or vital sign measurements common in the severely ill populations (such as electrolyte abnormalities, low blood pressure, hyperglycemia, etc.) that are part of the same clinical diagnosis (e.g., uncontrolled diabetic) can be recorded once with the worst grade for each adverse event (grade 3 and 4 only for this trial), with the start and stops dates of the intermittent syndrome. If there is clear resolution of the event, and then recurrence, it should be treated as a separate adverse event. Resolution is defined as return to baseline (either

normal if was normal at Day 1, or baseline (Day 1) grade if already an abnormality on the toxicity table at Day 1) for > 48 hours.

D-dimer and CRP should not be graded. There are collected on the same schedule as the safety laboratory tests (see SOA). However, they will be used in the assessment of study outcomes.

8.3.2 Definition of Serious Adverse Event (SAE)

An AE or suspected adverse reaction is considered serious (i.e., is an SAE) if, in the view of either the investigator or the Sponsor, it results in any of the following outcomes:

- Death;
- A life-threatening AE;
- Inpatient hospitalization or prolongation of existing hospitalization;
- A persistent or significant incapacity or substantial disruption of the ability to conduct normal life functions; or
- A congenital anomaly/birth defect.

Grade 4 AEs (potentially life-threatening events) are not always SAEs unless they are imminently life threatening.

Important medical events that may not meet the above criteria may be considered serious when, based upon appropriate medical judgment, they may jeopardize the subject and may require medical or surgical intervention to prevent one of the outcomes listed in this definition. Examples of such medical events include allergic bronchospasm requiring intensive treatment in an emergency room or at home, blood dyscrasias, convulsions that do not result in inpatient hospitalization, or the development of drug dependency or drug abuse.

“Life-threatening” refers to an AE that at occurrence represents an immediate risk of death to a subject. An event that may cause death if it occurs in a more severe form is not considered life-threatening. Similarly, a hospital admission for an elective procedure is not considered a SAE.

All SAEs, as with any AE, will be assessed for severity and relationship to study intervention.

All SAEs will be recorded on the AE CRF and reported to DMID (see Section 8.3.6).

All SAEs will be followed through resolution or stabilization by a licensed study physician (for IND studies, a physician listed on the Form FDA 1572 as the site PI or Sub-Investigator).

All SAEs will be reviewed and evaluated by DMID and will be sent to the DSMB (for periodic review), and the IRB/IEC.

8.3.3 Suspected Unexpected Serious Adverse Reactions (SUSAR)

Appendix B - ACTT-2: Baricitinib/Remdesivir vs Remdesivir

A SUSAR is any SAE where a causal relationship with the study product is at least reasonably possible but is not listed in the Investigator Brochure (IB), Package Insert, and/or Summary of Product Characteristics.

8.3.4 Classification of an Adverse Event

The determination of seriousness, severity, and causality will be made by an on-site investigator who is qualified (licensed) to diagnose AE information, provide a medical evaluation of AEs, and classify AEs based upon medical judgment. This includes but is not limited to physicians, physician assistants, and nurse practitioners.

8.3.4.1 Severity of Adverse Events

All AEs and SAEs will be assessed for severity using the DAIDS Table for Grading the Severity of Adult and Pediatric Adverse Events, version 2.1 (July 2017).

For AEs not included in the Table, the following guidelines will be used to describe severity. In addition, all deaths related to an AE are to be classified as grade 5 according to the DAIDS Table.

- Moderate (Grade 2): Events that are usually alleviated with additional specific therapeutic intervention. The event interferes with usual activities of daily living and causes discomfort but poses no significant or permanent risk of harm to the research subject.
- Severe (Grade 3): Events that interrupt usual activities of daily living, or significantly affect clinical status, or may require intensive therapeutic intervention. Severe events are usually incapacitating.
- Potentially life-threatening event (Grade 4): Events that are potentially life threatening.
- Deaths (Grade 5): All deaths related to an AE are classified as grade 5 (per DAIDS Table).

8.3.4.2 Relationship to Study Intervention

For each reported adverse reaction, the PI or designee must assess the relationship of the event to the study product using the following guideline:

- Related – There is a temporal relationship between the study intervention and event, and the AE is known to occur with the study intervention or there is a reasonable possibility that the study intervention caused the AE. Reasonable possibility means that there is evidence to suggest a causal relationship between the study intervention and the AE.
- Not Related – There is not a reasonable possibility that the administration of the study intervention caused the event, there is no temporal relationship between the study intervention and event onset, or an alternate etiology has been established.

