8.3.5.1 Investigator Reporting of AEs

Information on AEs will be recorded on the appropriate CRF. All clearly related signs, symptoms, and results of diagnostic procedures performed because of an AE should be grouped together and recorded as a single diagnosis. If the AE is a laboratory abnormality that is part of a clinical condition or syndrome, it should be recorded as the syndrome or diagnosis rather than the individual laboratory abnormality. Each AE will also be described in terms of duration (start and stop date), severity, association with the study product, action(s) taken, and outcome.

Any new infection that occurs on study, regardless of infecting agent (i.e., viral or non-viral) will be captured if it is a Grade 3 or 4 AE or SAE. Completion of the Infection Follow-up eCRF page is required for each infection reported as an adverse event or SAE with site of infection and source of culture provided, if available. The purpose is to document the occurrence of new infections by type of infection and not the duration of the new infections. Therefore, capture the first positive result(s) for the new infection (e.g., blood or urine culture, molecular diagnostic test result, etc.); there is no need to capture repeatedly positive results unless there is a new pathogen identified from the same site (e.g., blood) during the infection event. The sponsor will identify infections considered to be opportunistic based on Winthrop et al. 2015.

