8.3.6 Serious Adverse Event Reporting

8.3.6.1 Investigators Reporting of SAEs

Any AE that meets a protocol-defined criterion as an SAE that is judged to be related to either study product must be submitted within 24 hours of site awareness on an SAE form to the DMID Pharmacovigilance Group, at the following address:

DMID Pharmacovigilance Group
Clinical Research Operations and Management Support (CROMS)
[name]
[name]
SAE Hot Line: [name] (US) or [name] (outside US)
SAE [contact] (US) or [name] (outside US)
SAE Email Address: [contact]

Other supporting documentation of the event may be requested by the DMID Pharmacovigilance Group and should be provided as soon as possible. The DMID Medical Monitor will review and assess the SAE for regulatory reporting and potential impact on study subject safety and protocol conduct. At any time after completion of the study, if the site PI or appropriate sub-investigator becomes aware of an SAE that occurred during the subject's participation in the study, the site PI or appropriate sub-investigator will report the event to the DMID Pharmacovigilance Group.

SAEs that that are judged to be not related to study product are still captured on the AE case report form, but do not require separate reporting to the DMID Pharmacovigilance Group.

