9.4.4 Safety Analyses

Safety endpoints include death through Day 29, SAEs and Grade 3 and 4 AEs. These events will be analyzed univariately and as a composite endpoint. Time-to-event methods will be used for death and the composite endpoint. Each AE will be counted once for a given subject and graded by severity and relationship to COVID-19 or study intervention. AEs will be coded using the current version of the Medical Dictionary for Regulatory Activities (MedDRA). AEs will be presented by system organ class, duration (in days), start- and stop-date. Adverse events leading to premature discontinuation from the study intervention and serious AEs will be presented either in a table or a listing.

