Related SAE	x	x	x	x	x.x (x.x, x.x)
SAE with fatal outcome	x	x	x	x	x.x (x.x, x.x)
Related SAE with fatal outcome	x	x	x	x	x.x (x.x, x.x)
AE leading to discontinuation of study drug	x	x	x	x	x.x (x.x, x.x)
Related AE leading to discontinuation of study drug	x	x	x	x	x.x (x.x, x.x)
N = Number of subjects in the As Treated Population.					
^a Subjects are counted once for each category regardless of the number of events.					

Table 58: Adverse Events Occurring in 5% of Subjects in Any Treatment Group by MedDRA System Organ Class and Preferred Term, and Treatment Group - As Treated Population

Preferred Term	MedDRA System Organ Class	Baricitinib + RDV (N=X)			Placebo + RDV (N=X)			All Subjects (N=X)		
		n	%	Events	n	%	Events	n	%	Events
PT1	SOC1	x	x	x	x	x	x	x	x	x
Etc.	Etc.	x	x	x	x	x	x	x	x	x

N = number of subjects in the As Treated Population (number of subjects at risk).
n = number of subjects reporting event.
Events = total frequency of events reported.

Programming Notes:

Select all preferred terms/System organ classes where the % for any treatment group or overall is >= 5%.
Sort preferred terms by descending order of frequency.

Tables with similar format:

Table 59: Adverse Events Occurring in 5% of Subjects in Any Treatment Group by MedDRA System Organ Class and Preferred Term, and Treatment Group – Moderate Disease Severity, As Treated Population

Table 60: Adverse Events Occurring in 5% of Subjects in Any Treatment Group by MedDRA System Organ Class and Preferred Term, and Treatment Group – Severe Disease Severity, As Treated Population

Programming Notes for Tables 59 and 60: Actual disease severity will be used.

Table 61: Treatment-Emergent Renal Adverse Events by Preferred Term and Treatment Group – As Treated Population

Preferred Term	Baricitinib + RDV (N=X)			Placebo + RDV (N=X)			All Subjects (N=X)		
	n	%	Events	n	%	Events	n	%	Events
Any treatment-emergent hepatic adverse event	x	x	x	x	x	x	x	x	x
Glomerular filtration rate decreased	x	x	x	x	x	x	x	x	x
Blood creatinine increased	x	x	x	x	x	x	x	x	x
Acute kidney injury	x	x	x	x	x	x	x	x	x
Creatinine renal clearance decreased	x	x	x	x	x	x	x	x	x
Renal failure	x	x	x	x	x	x	x	x	x
Renal impairment	x	x	x	x	x	x	x	x	x
Proteinuria	x	x	x	x	x	x	x	x	x
Renal tubular necrosis	x	x	x	x	x	x	x	x	x
Blood creatinine abnormal	x	x	x	x	x	x	x	x	x
Continuous haemodiafiltration	x	x	x	x	x	x	x	x	x
Glomerular filtration rate abnormal	x	x	x	x	x	x	x	x	x

N = Number of subjects in the As Treated Population.

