APPENDIX 3. LISTINGS MOCK-UPS**TABLE OF LISTINGS**

Listing 1: Exclusions from the As Treated Population	125
Listing 2: Subjects who Early Terminated or Discontinued Treatment.....	126
Listing 3: Subject-Specific Protocol Deviations	127
Listing 4: Non-Subject-Specific Protocol Deviations.....	128
Listing 5: Individual Efficacy Response Data: Clinical Status Score Data	129
Listing 6: Individual Efficacy Response Data: NEWS	130
Listing 7: Demographic Data	131
Listing 8: Pre-Existing and Concurrent Medical Conditions.....	132
Listing 9: Concomitant Medications.....	133
Listing 10: Medications of Interest	134
Listing 11: Compliance Data	135
Listing 12: Listing of Non-Serious Adverse Events	136
Listing 13: Listing of Related Adverse Events	137
Listing 14: Listing of Non-Fatal Serious Adverse Events	138
Listing 15: Listing of Infections.....	139
Listing 16: Listing of Deaths.....	140
Listing 17: Pregnancy Reports – Maternal Information	141
Listing 18: Pregnancy Reports – Gravida and Para	142
Listing 19: Pregnancy Reports – Live Birth Outcomes	143
Listing 20: Pregnancy Reports – Still Birth Outcomes	144
Listing 21: Pregnancy Reports – Spontaneous, Elective, or Therapeutic Abortion Outcomes	145
Listing 22: Clinical Laboratory Results.....	146
Listing 23: Physical Exam Findings	147
Listing 24: Subjects who Received the Incorrect Treatment	148
Listing 25: Subjects Randomized to the Incorrect Disease Severity Stratum.....	148

Listing 1: Exclusions from the As Treated Population

Randomized Treatment Group	Actual Disease Severity	Subject ID
Baricitinib + RDV/ Placebo + RDV	Moderate / Severe	XXXXX

Programming Notes: Include randomized subjects only. Sort Order = Treatment Group, Disease Severity, USUBJID.

Listing 2: Subjects who Early Terminated or Discontinued Treatment

Actual Treatment Group	Actual Disease Severity	Subject ID	Category	Treatment Discontinued	Reason for Early Termination or Treatment Discontinuation	Study Day
Baricitinib + RDV/ Placebo + RDV	Moderate / Severe	XXXXX	Early Termination/Treatment Discontinuation	NA/Infusions/Tablets/Infusions + Tablets	Xxxxxx	xxxx

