Note: If medication started prior to enrollment and there is no date, then Medication Start Day = Prior to Enrollment

If medication is ongoing at end of study, the Medication End Day = Ongoing

Listing 10: Medications of Interest

Actual Treatment Group	Actual Disease Severity	Subject ID	Medication Number	Medication	Medication Start Day	Medication End Day	Indication	Medication of Interest Category	Medication of Interest Subcategory
Baricitinib + RDV/ Placebo + RDV	Moderate/ Severe	xxx	xx	xxxx	x	x	xxxx	xxxx	xxxx

Programming Notes: Sort Order = Treatment Group, Actual severity, USUBJID, CM number

Note: If medication started prior to enrollment and there is no date, then Medication Start Day = Prior to Enrollment

If medication is ongoing at end of study, the Medication End Day = Ongoing

If the medication does not have an applicable subcategory, then display 'N/A'

Listing 11: Compliance Data

Dose Number	Infusions				Tablets		Reason for Missed Dose	Comments
	Infusion Administered?	Infusion Slowed or Stopped?	Reason(s) for Slowed/Stopped Infusion	Volume Administered if Slowed/Slowed (mL)	Number of Tablets Administered	Tablet Administered Successfully?		
Actual Treatment Group: , Actual Disease Severity: , Subject ID: , Study Day of Discharge: , Study Day of Death:								
1	Yes/No	No/Yes (Slowed)/Yes (Stopped)	Xxxxx / NA	Xxx	2/1	Yes/No	Xxx/NA	
2	Yes/No	No/Yes (Slowed)/Yes (Stopped)	Xxxxx / NA	Xxx	2/1	Yes/No	Xxx/NA	
...	

Programming Notes: Sort Order = Treatment Group, Actual severity, USUBJID. If columns do not fit within the eCTD specified margins, then Study Day of Discharge and Study Day of Death can be added to the header row after Subject ID.

Listing 12: Listing of Non-Serious Adverse Events

Adverse Event	Study Day	Duration	Severity	Relationship to Study Treatment	If Not Related, Alternative Etiology	Unanticipated Problem	Action Taken with Study Treatment	Subject Discontinued Due to AE	Outcome	MedDRA System Organ Class	MedDRA Preferred Term
Actual Treatment Group: Actual Disease Severity: , Subject ID: , AE Number:											
xxx	xx	x	xxx	Related/Not Related	xxxx	Yes/No	xxx	Yes/No	xxxx	xxxx	xxxx
Comments: xxxx											

Programming Note: Sort order will be Treatment Group, Actual severity, USUBJID, AE Number.

Listing 13: Listing of Related Adverse Events

Adverse Event	Study Day	Duration	Severity	Unanticipated Problem	Action Taken with Study Treatment	Subject Discontinued Due to AE	Outcome	MedDRA System Organ Class	MedDRA Preferred Term

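### Relatedness and AE-related stopping are not split between open-label remdesivir and the blinded tablets, which dilutes two descriptive safety contrasts and hides how often the oral product was blamed or stopped

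*Protocol*

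**What the plan says.** Appendix B of the protocol gives each subject two products: remdesivir, which is not blinded and goes to both arms, and blinded baricitinib or placebo tablets (6.3.2). The tablets also have their own list of stopping conditions (7.1.1.2).

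Causality is nevertheless a single judgement. Section 8.3.4.2 reads: "For each reported adverse reaction, the PI or designee must assess the relationship of the event to the study product using the following guideline", with the two answers Related and Not Related. Section 8.3.5.1 has each AE described by "severity, association with the study product, action(s) taken, and outcome". SAE reporting in 8.3.6.1 does recognise two products, but pools them: "Any AE that meets a protocol-defined criterion as an SAE that is judged to be related to either study product" triggers the SAE form.

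The SAP follows suit. The AE listings that report causality carry one column, "Relationship to Study Treatment". Tables 56, 57 and 63 count related AEs with no product named. Tables 56 and 57 count AEs leading to discontinuation of study drug; one Table 57 row is "Related AE leading to discontinuation of study drug", shown with a risk difference and 95% CI.

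The product that was stopped is recorded elsewhere. Listing 2 has a column with the values "NA/Infusions/Tablets/Infusions + Tablets", next to the reason and the study day.

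**The concern.** The wording of 8.3.4.2 is the same as in Appendix A (ACTT-1), where there was only one active product. In ACTT-2 the only randomised difference is baricitinib versus placebo, so the safety reader will want to know how often the oral product was blamed for an event and how often it was stopped because of one. The related-AE and discontinuation rows cannot say. An event attributed to remdesivir counts as related in either arm, and a subject whose infusions were stopped may be counted together with one whose tablets were stopped.

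Two features make this more than wording. The protocol describes liver-enzyme changes for both drugs (Appendix B 2.2.2.1 and 2.2.3.1), so attribution is a live question. And discontinuation or temporary suspension of study product is a listed safety measure (Appendix B section 3; SAP 3.1).

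**Working it through.** **Terms.** The documents do not define study product or study drug, and their use varies:

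| Place | What the term covers |
|---|---|
| Protocol App. B 7.4 (readmission) | Study product: infusion and oral product |
| Protocol App. B 8.3.6.1 | Either study product: both |
| SAP 6.3.1 (As Treated) | Study product: baricitinib/placebo only |
| Protocol App. B 6.1.4, oral section | Study drug: the tablets, from context |
| SAP Tables 56 and 57 | Study drug: not stated |

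The discontinuation rows could therefore mean either product or only the tablets. SAP Table 4, by contrast, gives compliance separately for remdesivir and for the oral product.

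**Effect of pooling.** The plan states no figure on this point, so there is none to reproduce. The only document input is the planned total of 1032 (SAP section 5), so 1032 / 2 = 516 per arm. The event rates below are assumptions made for illustration.

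Let pX be the risk of an AE attributed to the oral product (4% on baricitinib, 2% on placebo), and pR the risk of an AE attributed to remdesivir, equal in both arms and independent of pX.

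- Pooled risk = 1 − (1 − pR)(1 − pX)
- Risk difference (RD) = (1 − pR)(0.04 − 0.02)
- Standard error (SE) = √(Σ p(1 − p) / 516); half-width = 1.96 × SE
- Power = Φ(RD / SE − 1.96)

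Separate recording (pR = 0): SE = √((0.0384 + 0.0196) / 516) = 0.0106, so the half-width is 2.1 points. Power = Φ(0.0200 / 0.0106 − 1.96) = 47%.

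Pooled, pR = 3%: risks are 1 − 0.97 × 0.96 = 6.88% and 1 − 0.97 × 0.98 = 4.94%.

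Pooled, pR = 8%: risks are 1 − 0.92 × 0.96 = 11.68% and 1 − 0.92 × 0.98 = 9.84%.

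| pR | Baricitinib arm | Placebo arm | RD (points) | Half-width (points) | Risk ratio | Power |
|---|---|---|---|---|---|---|
| 0 (separate) | 4.0% | 2.0% | 2.0 | 2.1 | 2.00 | 47% |
| 3% | 6.9% | 4.9% | 1.9 | 2.9 | 1.39 | 26% |
| 8% | 11.7% | 9.8% | 1.8 | 3.8 | 1.19 | 16% |

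A second set of assumed rates (5% versus 2%) shows the same pattern. With a 10% common rate the difference moves from 3.0 to 2.7 points, the half-width from 2.2 to 4.1, and the ratio from 2.50 to 1.23.

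**Direction.** The RD formula shows that pooling cannot create a difference: if the two pX values are equal, RD is 0 at any pR. A true difference is multiplied by (1 − pR), a small shrinkage at these rates. The larger cost is the added variance.

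**The case against.** A reader might infer that the related-AE and discontinuation comparisons cannot isolate baricitinib, or are confounded by remdesivir. The documents do not support that. Allocation is 1:1, remdesivir is common to both arms and the tablets are blinded, so the between-arm difference estimates the effect of adding baricitinib, which is the trial's stated comparison. This objection stands in full.

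The main safety comparisons also use no attribution. SAP 9.4 compares Grade 3 or 4 AEs and SAEs by Barnard's exact test, analyses a time-to-event composite, and summarises infections by arm; 9.6 covers laboratory results. Venous thromboembolism is reportable whatever its cause (Appendix B 8.3.1). This also stands, and it limits the point to a few descriptive rows. Table 57 plans no p-value and reports risk differences rather than ratios, so the power and ratio columns above describe dilution and do not bear on any planned test.

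On discontinuation, Protocol 9.4.4 says that "Adverse events leading to premature discontinuation from the study intervention" may go in a table or a listing, and Listing 2 already separates the products. That meets the letter of the protocol. It still leaves Table 57 attaching a CI to an undefined count.

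Three further points stand in part. The AE CRF and the SAE form are not in the documents and may already record relatedness by product; if so, the protocol and SAP should say so and use it. The manufacturer's addendum SAP, announced in SAP 2.1 for additional safety analyses, may contain product-specific summaries. And attribution between two drugs given together is imperfect: investigators know that everyone receives remdesivir but not who receives baricitinib, so they may lean towards blaming remdesivir.

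Expectedness for a SUSAR (8.3.3) is judged against product reference documents, but nothing prevents the medical monitor from doing this product by product under 8.3.6.1.

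**Conclusion.** The point holds as a minor one. The protocol and SAP show one relatedness judgement against an undefined study product, and AE-related stopping counted for an undefined study drug, in a trial where each subject has two products that can be stopped separately. The between-arm differences remain unbiased for adding baricitinib. Remdesivir-attributed events common to both arms dilute the related-AE contrast and, if study drug means either product, the discontinuation contrast as well. Neither table can show how often the oral product was blamed or stopped.

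The size is illustrative only: a half-width of 2.9 to 3.8 points in place of 2.1, at assumed oral-product risks of 4% and 2% with 3% to 8% common events. It rests on those rates, on independent causes, and on 516 treated per arm; the As Treated population may be slightly smaller.

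**What to change.** 1. **SAP Tables 56 and 57:** add a row for AEs leading to discontinuation of the oral study product, in Table 57 with risk difference and 95% CI. Build it from the product-stopped field and the reason already in Listing 2. This needs no new data, provided the recorded reason identifies an AE.
2. **Definitions:** state in the protocol and the SAP what study product and study drug cover, and apply this to every safety table and listing.
3. **Protocol Appendix B 8.3.4.2 and 8.3.5.1, and the AE CRF if it does not already do so:** record relatedness separately for remdesivir and for the oral study product, allowing an event to be marked as related to both.
4. **SAP Tables 56, 57 and 63:** add rows for AEs related to the oral study product. A row for related AEs leading to discontinuation of the oral product depends on item 3.
5. Keep the pooled rows, which also capture events attributed to the combination.

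The cost is one CRF item and a few table rows. The per-product rows should be read with the caveat that investigators cannot always separate two drugs given together. No dosing or stopping rule changes.
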